9.4.3. Change from Baseline

Change from baseline will be calculated as the baseline value subtracted from the value at a particular time point. If one of the values is missing and there are no pre-specified missing value imputation rules (see [Section 7.2.1.1](#)), then a change from baseline will not be calculated.

9.4.4. Analysis Visits

Summaries over postbaseline time points or analyses at specific postbaseline time points will be performed based on the list of visits described in the schedule of assessment of the protocol. For all assessments, the number of days from baseline will be calculated using the following formula: (date of assessment) - (date of first study treatment) + 1. This number of days will be used to assign analysis visit. This may not always correspond to the electronic case report form (eCRF) visit.

The analysis visit assignment for a specific assessment will be based on visit windows around each scheduled visit for that specific assessment. The windows for each scheduled visit will go from the midpoint (in days) between the current visit and the previous scheduled visit to the midpoint between the current visit and the subsequent scheduled visit. If the interval separating 2 scheduled visits is an even number of days, that middle day will be included in the later visit window and excluded from the prior visit window. For example, for an assessment with a scheduled visit Day 127, and a prior scheduled visit Day of 113 and subsequent scheduled visit Day of 141, the window will start at 120 days from baseline and will go to 133 days from baseline.

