- ^p Urine sample for drug measurement will be collected at end of infusion (EOI) (within 0.5 hours after the EOI) on Days 1, 15, and 71; and at any time on Day 29.
- ^q Collection will be predose.
- ^r A single whole blood collection from those patients who consent to genetic testing can be collected anytime during the study.
- ^s ADA serum samples will be collected predose on Days 1, 71, and 127. Day 183 collection will occur prior to first dose in the Extension Period. Early termination collection will occur at any time on the ET visit day. All collection times will be recorded in the eCRF.
- ^t Review the Clinical Trial Participant Safety Information Card with the patient and discuss the importance of carrying the safety card at all times, and the risks ALXN1210 treatment, including the risk of meningococcal infection.
- ^u Concomitant medications must be collected at all study visits and checked against the prohibited medication listed in [Section 9.7](#).

Table 1: Schedule of Study Visits and Assessments: Screening Through End of Initial Evaluation Period (Continued)

^v The dose of ALXN1210 is based on the patient's last recorded study visit body weight (Day 1 dosing is based on the body weight at Screening).

^w If a local laboratory is used to define eligibility, additional samples will be collected during the Screening Period for LDH, platelet count, hemoglobin and serum creatinine and tested at the central laboratory.

^x The primary efficacy endpoint assessment is before dosing on Day 183. Dosing on Day 183 is the start of the Extension Period. Please refer to additional Day 183 postdose assessments in [Table 2](#).

Table 2: Schedule of Study Visits and Assessments: Extension Period Day 183 to Day 911

Period	Extension Period													
	183 ^p	239	295	351	407	463	519	575	631	687	743	799	855	911
Study Day	±2	±7	±7	±7	±7	±7	±7	±7	±7	±7	±7	±7	±7	±7
Window (day)	±2	±7	±7	±7	±7	±7	±7	±7	±7	±7	±7	±7	±7	±7
Weight		X	X	X	X	X	X	X	X	X	X	X	X	X
Pregnancy test ^a	X	X	X	X	X	X	X	X	X	X	X	X	X	X
FACIT-Fatigue questionnaire /Pediatric FACIT-Fatigue questionnaire ^{b,c}				X				X			X			X
EQ-5D-3L questionnaire ^c				X				X			X			X
Patient-reported aHUS symptoms questionnaire ^c		X	X	X	X	X	X	X	X	X	X	X	X	X
Resource utilization patient questionnaire ^c		X	X	X	X	X	X	X	X	X	X	X	X	X
Abbreviated physical examination ^d		X	X	X	X	X	X	X	X	X	X	X	X	X
Assessment of extra-renal signs or symptoms of aHUS		X	X	X	X	X	X	X	X	X	X	X	X	X
Vital signs ^e		X	X	X	X	X	X	X	X	X	X	X	X	X

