7.2.1. Primary Analysis

The primary efficacy endpoint is Complete TMA Response during the 26-week Initial Evaluation Period. The primary analysis will consist in estimating the proportion of complete TMA responders among ALXN1210 treated patients. This will be performed by calculating the point estimate and a 2-sided 95% confidence interval (CI) for the proportion of complete TMA responders in ALXN1210 treated patients, where the numerator will be the number of patients achieving complete TMA response during the 26-week Initial Evaluation Period and the denominator will be the number of patients in the FAS. The CI will be based on the asymptotic Gaussian approximation method with a continuity correction.

The criteria for Complete TMA response are presented in [Section 5.1.1](#). Patients must meet all Complete TMA Response criteria at 2 separate assessments obtained at least 4 weeks (28 days) apart, and any measurement in between. To be considered a responder during the 26-week Initial Evaluation Period, the latest time point a patient can first meet the response criteria is 28 days before the Day 183 assessment.

Formal statistical comparison analyses are not planned for this estimation study. Results from ALXN1210 treated patients will be evaluated in the context of results observed in patients treated with eculizumab in prospective eculizumab studies.

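### The SAP's Day 183 analysis window has no cut at the first Extension dose and runs to Day 210 for the primary laboratories, so post-dose values can be labelled Day 183

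*SAP*

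**What the plan says.** SAP 9.4.4 assigns every assessment to an analysis visit by its day count, and notes that the result may differ from the eCRF visit. Assignment is "based on visit windows around each scheduled visit for that specific assessment". On the lower side, "The windows for each scheduled visit will go from the midpoint (in days) between the current visit and the previous scheduled visit"; on the upper side, the window runs "to the midpoint between the current visit and the subsequent scheduled visit". For an even interval, "that middle day will be included in the later visit window and excluded from the prior visit window". The section names no exception at the end of the Initial Evaluation Period.

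SAP 9.4.5 then keeps one value per analysis visit: the one nearest the scheduled day, or the earlier of two equally near. It does not ask whether a value came before or after a dose.

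The protocol draws the period boundary explicitly. Table 1, footnote x, in section 7.3 states: "The primary efficacy endpoint assessment is before dosing on Day 183. Dosing on Day 183 is the start of the Extension Period". The footnotes to the same table make the Day 183 ECG predose and put the Day 183 antidrug-antibody (ADA) sample ahead of the first Extension dose.

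For the primary endpoint, SAP 7.2.1 says that "the latest time point a patient can first meet the response criteria is 28 days before the Day 183 assessment". It does not say whether that assessment is the actual predose visit or whatever value 9.4.5 selects for the Day 183 analysis visit.

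**The concern.** Day 183 is both the last assessment of the Initial Evaluation Period and the day of the first Extension infusion. Visits are one or two weeks apart up to that point and eight weeks apart afterwards. A midpoint rule without a cut therefore stretches the Day 183 window mostly forwards, into the Extension Period.

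Two things are at stake. A by-visit summary at Day 183 (response over time, eGFR, hematology, quality of life, ADA, ECG) can contain values collected after the period it is meant to describe. And, on one reading of SAP 7.2.1, a response not confirmed within 26 weeks could be counted in the primary proportion.

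**Working it through.** **Inputs.** The window and selection rules come from SAP 9.4.4 and 9.4.5. Visit days come from Protocol Tables 1 to 3 and their footnotes.

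- Chemistry and hematology: 155, 169, 183, then 239
- Quality of life and ADA: 127, 183, then 351
- ECG: 57, 183, then 1863 (current protocol)
- Visit tolerance: ±2 days at Day 183, ±7 days in the Extension Period

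**Formula.** All these intervals are even, so lower limit = (previous + current)/2 and upper limit = (current + next)/2 − 1.

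**The SAP's own example.** For Day 127 with neighbours 113 and 141: (113 + 127)/2 = 120 and (127 + 141)/2 − 1 = 133. The SAP says "the window will start at 120 days from baseline and will go to 133 days from baseline", so the formula reproduces it.

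**Day 183.**

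| Assessment | Lower limit | Upper limit | Days past Day 185 |
|---|---|---|---|
| Laboratories | (169 + 183)/2 = 176 | (183 + 239)/2 − 1 = 210 | 25 |
| Quality of life, ADA | (127 + 183)/2 = 155 | (183 + 351)/2 − 1 = 266 | 81 |
| ECG | (57 + 183)/2 = 120 | (183 + 1863)/2 − 1 = 1022 | 837 |

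Day 185 is the reference because a visit on Day 184 or 185 is within tolerance and may be an ordinary predose visit.

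The ECG limit depends on the current protocol schedule, whereas SAP section 4 still describes an Extension of up to 2 years. If the next ECG were on Day 911 (an assumption), the limit would be (183 + 911)/2 − 1 = 546.

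**Which value is kept (SAP 9.4.5).**

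- Draws on Days 183 and 200: Day 183 is kept.
- Draw on Day 200 only: Day 200 is kept.
- Predose visit and dose on Day 181, unscheduled draw on Day 184: distances are 2 and 1, so the post-dose Day 184 value is kept.
- Draws on Days 181 and 185: distances tie at 2, so Day 181 is kept.

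A post-dose value is thus selected when the predose value is missing, excluded or further away. Exclusion can follow from table-top hemolysis (SAP 5.2.3), dialysis for creatinine (9.4.9) or platelet transfusion (9.4.10).

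**Where late draws come from.** The first in-window Extension visit is Day 239 − 7 = 232. Laboratory values on Days 186 to 210 therefore come only from unscheduled, early-termination or out-of-window visits. Protocol 7.3 permits unscheduled visits and requires a central duplicate when a local laboratory is used.

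**Primary endpoint, if the Day 183 assessment means the analysis visit.**

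- First met on Day 169, Day 183 value available: 183 − 169 = 14 days, so not confirmed.
- First met on Day 169, Day 183 value unusable: the 28-day gap is reached on Day 169 + 28 = 197. A sole later draw on Days 197 to 210 that meets the criteria confirms the response.
- With neither an on-time nor a late draw, SAP 7.2.1.1 does not allow a value carried forward from the initial assessment to confirm. The window can grant a response that the missing-data rule would refuse.
- Latest first-met day: the Day 169 window is (155 + 169)/2 = 162 to (169 + 183)/2 − 1 = 175. A value on Day 175 needs confirmation on Day 175 + 28 = 203 or later, so on Days 203 to 210.

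**The case against.** The strongest reply is that the primary endpoint is already bounded. It is defined as response within the Initial Evaluation Period, the protocol puts its last assessment before the Day 183 dose, and SAP 9.4.4 is written for summaries over time and analyses at particular time points. On that reading late values never reach the primary analysis. This stands as a reasonable reading, and it makes the primary-endpoint part an ambiguity rather than a certain error. It does not define the Day 183 assessment in SAP 7.2.1, and it gives no protection to the by-visit summaries, which 9.4.4 does govern.

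It is also fair that the circumstances are uncommon. A value on Day 183 itself always wins, and no scheduled in-window visit falls between Days 186 and 231.

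Some stronger inferences are not supported:

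- **First-met day as late as 182.** A reader might compute 210 − 28 = 182. Days 182 and 210 both fall in the Day 183 window, and 9.4.5 keeps only Day 182, so Day 210 cannot confirm it. With one value per analysis visit the limit is Day 175.
- **Late values always carry an extra dose.** Patients who stop treatment but stay in the study (Protocol 8.3.2) have no Extension dose, and a late Day 183 visit may still be predose.
- **Early-termination ECGs are lost.** They may be labelled Day 183 in the by-visit table, but SAP 7.3.3.3.1 keeps them in the listings and in the worst-on-study shift table. ADA ever-positive status (7.3.3.3.2) likewise does not depend on windows.

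**Conclusion.** The point holds. Taken literally, SAP 9.4.4 lets values drawn after the first Extension dose be labelled Day 183, in conflict with the protocol's placement of the primary assessment before that dose. The by-visit Week 26 summaries are exposed most directly. The primary endpoint is exposed only if the Day 183 assessment in SAP 7.2.1 is read as the analysis visit.

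The likely effect is small. The documents give no rate of missing or excluded Day 183 values, so the number of patients cannot be computed, but the conditions needed suggest few. Each would move the primary proportion by about 1.8 percentage points (1/55, assuming all 55 planned patients are in the Full Analysis Set).

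The laboratory, quality-of-life and ADA limits rest on the current Tables 1 and 2. The ECG limit of Day 1022 also rests on Table 3 and would be shorter under the 2-year Extension that the SAP describes.

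**What to change.** - **SAP 9.4.4:** end the Day 183 window at the predose assessment of the first Extension infusion or, if no Extension dose is given, at Day 185 (the +2 visit tolerance).
- **SAP 7.2.1:** state that no value after that cut can start or confirm the 26-week response.
- **Values after the cut but before the next visit's own midpoint window:** list them as unscheduled. Moving them to the next Extension visit would only shift the mislabelling: a Day 186 laboratory value would appear as Day 239, 53 days early.
- **Early termination:** show ECG, quality-of-life and ADA results from these visits under a separate early-termination time point.

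The cost is a few sentences of SAP text and a programming condition. The downside is that a few Day 183 values remain missing. If the 26-week analysis has already been run, a listing of Day 183 values dated after the first Extension infusion would show whether any result is affected.

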9.4.5. Analysis Value

The values being considered for analysis at a specific postbaseline time point will be based on the analysis visit assigned to that value. If there is more than one non-missing value for a specific assessment with the same analysis visit, the value used for analysis will be the one for which the calculated number of days from baseline is closest to the scheduled visit day. If two values have the same analysis visit and are the same distance away from the scheduled visit day, the earlier of the 2 values will be used for analysis.

9.4.6. Adverse Events

The analysis of Adverse Events is described in detail in [Section 7.3.2](#).

Treatment-emergent AEs (TEAEs) are events with start dates and start times on or after the date and time of the first study drug dose. If the start date of an AE is partially or completely missing and the end (stop) date and time of the AE does not indicate that it occurred prior to first dose, then the determination of treatment-emergent status will be based on the following:

- If the start year is after the year of the first study drug dose, then the AE is treatment-emergent; else,

- If the start year is the same as the year of the first study drug dose and
 - the start month is missing, then the AE is treatment emergent; else if
 - the start month is present and is the same or after the month of the first study drug dose, then the AE is treatment-emergent; else,
- If the start date is completely missing, then the AE is treatment-emergent.

All other AEs are considered PreTreatment Adverse Events (PTAEs).

Related AEs are defined as possible, probable or definitely related. Unrelated AEs are defined as unlikely or not related.

9.4.7. Adverse Events Related to Meningococcal Infection

To find meningococcal events, the adverse event dataset will be searched for the following MedDRA Preferred Terms: Meningitis meningococcal, Meningococcal bacteraemia, Meningococcal infection, Meningococcal sepsis, Meningococcal carditis, Encephalitis meningococcal, Endocarditis meningococcal, Myocarditis meningococcal, Optic neuritis meningococcal, and Pericarditis meningococcal. In addition, a medical review will be done to ensure that no relevant events were missed.

9.4.8. Concomitant Medications/Therapies

The analysis of concomitant medications and therapies is described in detail in [Section 7.1.4](#).

Concomitant medications or therapies are defined as any non-study medications or therapies that were taken or given while the patient also received study medication. A medication or therapy will be considered concomitant if the start date is on or after the date of the first study drug infusion, or if the start date is before the first infusion date and the end (stop) date is after the first infusion date. If the start date of a medication/therapy is partially or completely missing and the end (stop) date of the medication/therapy does not indicate that it ended prior to first infusion, then the determination of the concomitant status will be based on the following:

- If the start year is after the year of the first study drug infusion, then the medication/therapy is concomitant; else,
- If the start year is the same as the year of the first study drug infusion and
 - the start month is missing, then the medication/therapy is concomitant; else if
 - the start month is present and is the same or after the month of the first study drug infusion, then the medication/therapy is concomitant; else,
- If the start date is completely missing, then the medication/therapy is concomitant.

All other medications/therapies are considered Prior Medications/Therapies.

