7.1.2. Protocol Deviations

Important protocol deviations will be determined per the standard operating procedure (SOP) “Identification, Handling, and Documentation of Protocol Deviations” (SOP-G-CL-0044). The number and percent of patients with specific protocol deviations will be summarized for all enrolled patients by major and minor deviations.

To ensure completeness of the list of important protocol deviations, the following will be identified programmatically from the database:

1. Patients from whom informed consent was not obtained
2. Patients who violated any inclusion/exclusion criteria
3. Patients who took prohibited medications or underwent any prohibited procedure
4. Patients who received less than 100% of the protocol specified number of doses of study drug during the Initial Evaluation Period
5. Patients found not to satisfy one or more of the following inclusion/exclusion criteria (Inclusion Criterion number 2c or Exclusion Criteria numbers 1 and 2) whom are not discontinued from the study.

A by-patient listing of inclusion/exclusion criteria, as well as protocol deviations will be presented, separately.

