7.1.4. Prior and Concomitant Medications / Nonpharmacologic Procedures

Prior and concomitant medications (including vitamins and herbal preparations) will be coded using the World Health Organization Drug Dictionary (WHO-DRUG), while prior and concomitant nonpharmacologic therapies and procedures (any therapeutic intervention, such as surgery/biopsy or physical therapy) will be coded using MedDRA.

Prior medications or procedures are defined as any non-study medications or procedures that were started, and were stopped, prior to the date of first infusion. Concomitant medications or procedures are defined as any non-study medications or procedures that were taken or occurred while the patient also received study medication. Prior and concomitant summaries will be presented separately.

Medications will be summarized by Anatomic-Therapeutic-Chemical (ATC) level 4 class and preferred drug name using frequency counts and percentages of patients for the Safety Set. Procedures will be summarized similarly, but by MedDRA Class and preferred term.

A table summarizing pretreatment plasma exchanges and plasma infusion as well as kidney dialysis will be generated. A similar table will summarize concomitant kidney dialysis.

In the event a patient receives a prohibited medication or undergoes a prohibited procedure, this will be reported as a protocol deviation as described in [Section 7.1.2](#).

By-patient listings of these data will be provided separately.

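### SAP 9.4.8 classes a continuing therapy as prior when its partial start date is known to precede the month of first infusion, so the concomitant tables would understate background treatment

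*SAP*

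**What the plan says.** SAP 7.1.4 defines prior items as those that "were started, and were stopped, prior to the date of first infusion", and concomitant items as those that "were taken or occurred while the patient also received study medication". The two groups are summarised separately for the Safety Set, and the section also plans a table of concomitant kidney dialysis.

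SAP 9.4.8 opens with the same idea of overlap: concomitant means "any non-study medications or therapies that were taken or given while the patient also received study medication". With known dates, a therapy is concomitant if it starts on or after the day of first infusion, "or if the start date is before the first infusion date and the end (stop) date is after the first infusion date".

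A partial or missing start date has its own branch. It is entered when "the end (stop) date of the medication/therapy does not indicate that it ended prior to first infusion". Status is then decided by a list in which the therapy is concomitant if:

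- the start year is later than the first-infusion year;
- the start year is the same and the month is missing;
- the start year is the same and "the start month is present and is the same or after the month of the first study drug infusion"; or
- the start date is missing altogether.

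Whatever matches none of these goes to the residual line: "All other medications/therapies are considered Prior Medications/Therapies".

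**The concern.** Whether a therapy is concomitant depends on whether it overlaps with study drug, so the stop date matters. The partial-date list uses the stop date only as an entry condition and then tests the start date alone. It has the same structure as the adverse event rule in SAP 9.4.6, where onset is the right test. Applied to medications, it sends some therapies to prior precisely because they are known to have begun before first infusion, even though nothing shows that they stopped.

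Such therapies are plausible in this trial. The protocol plans 10 to 25 kidney transplant recipients among about 55 patients, and Protocol 9.7 allows continued antirejection treatment and the tapering of steroids begun empirically before enrolment. Both start before Day 1 and run on. If the start date is partial, the record lands in the wrong table. A reader of a single-arm study, whose results are to be set against earlier eculizumab studies, would see less on-study background therapy than patients received.

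**Working it through.** No sample size or precision figure bears on this point. The check applies SAP 9.4.8 as written and compares the result with 7.1.4.

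**Inputs.** The classification rules come from SAP 9.4.8 and 7.1.4. A first infusion on 15 June 2017 is assumed for illustration. Eight start-date patterns were crossed with four stop patterns: ongoing with no stop date, stopped 1 September 2017, stopped on 15 June 2017 itself, and stopped 1 June 2017. UN means unknown.

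**Rule in 7.1.4.** Prior if the therapy started and stopped before 15 June 2017; otherwise not prior.

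**Rule in 9.4.8, partial or missing start date.** If the stop date is before 15 June 2017, prior. Otherwise concomitant if the year is after 2017, or the year is 2017 with the month missing or June or later, or the date is wholly missing. Otherwise prior.

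**Result for a therapy that stops on 1 September 2017:**

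| Start date | 9.4.8 as written | 7.1.4 |
|---|---|---|
| 10 Mar 2015 | Concomitant | Not prior |
| Mar 2015, day UN | **Prior** | Not prior |
| 2015, month UN | **Prior** | Not prior |
| 20 May 2017 | Concomitant | Not prior |
| May 2017, day UN | **Prior** | Not prior |
| Jun 2017, day UN | Concomitant | Not prior |
| 2017, month UN | Concomitant | Not prior |
| Wholly missing | Concomitant | Not prior |

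The six partial or missing rows come out the same when the therapy is ongoing or stops on 15 June 2017. Of those six patterns, three conflict with 7.1.4 under each of the three continuing stop patterns: 3 × 3 = 9 of 6 × 3 = 18 combinations. This counts cases in the rule, not patient records.

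**What the table shows.** A therapy started on 10 March 2015 and stopped on 1 September 2017 is concomitant. Lose the day of the start date and it becomes prior. Lose the whole start date and it is concomitant again. Nothing about the overlap has changed.

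**Complete start dates.** Two further gaps appear for the starts on 10 March 2015 and 20 May 2017:

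- If the therapy is ongoing, it has no stop date later than first infusion. Read literally, it is prior; it is concomitant only if the programmer treats ongoing as later.
- If the therapy stops on 15 June 2017, 9.4.8 makes it prior because the stop must be after the infusion date. Section 7.1.4 does not, because the stop must be before it.

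**Where the rules agree.** Therapies that stopped on 1 June 2017 are prior under both sections for every start pattern before first infusion.

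**The case against.** The best defence is that the intent is clear. Section 9.4.8 opens with the overlap definition and refers to 7.1.4 for detail. A start year of 2015 is plainly before June 2017, so the known-date sentence could be said to cover it already. That reading would remove the fault for therapies with a later stop date, but the text does not support it: partial start dates are expressly referred to the list, and the list ends with a catch-all. A programmer following 9.4.8 would code the wrong class.

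A second defence is that a misclassified record is moved, not lost. It still appears in the prior summary and the by-patient listings, and no efficacy analysis uses the classification. This stands, and it limits the consequence to descriptive tables.

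A reader might infer more: that these therapies also escape the prohibited-treatment check, so that patients stay wrongly in the Per Protocol Set. The documents do not support this.

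- SAP 7.1.2 lists "Patients who took prohibited medications or underwent any prohibited procedure" among deviations identified programmatically from the database, and SAP 6.2 refers to Protocol 9.7. Neither mentions the prior or concomitant class.
- Protocol 9.7 frames prohibition by time after first dose, and the footnotes to the Schedule of Assessments have medications checked against the prohibited list at each visit.
- Protocol 9.7 permits the likeliest examples: antirejection regimens already in place and empirical steroids being tapered.
- SAP 7.1.2 separately flags any breach of the entry criteria, which cover chronic immunoglobulin or rituximab, other immunosuppression and complement inhibitors.

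The check would be weakened only if the programming filtered on this class, which the documents leave open but do not state.

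A reader might likewise infer that dialysis handling is compromised. Chronic dialysis is excluded at entry. The only prohibited dialysis is new dialysis in the first 48 hours after first dose, which cannot have started in an earlier month. Baseline creatinine, exclusion of creatinine values, eGFR imputation and dialysis status (SAP 9.4.2, 9.4.9 and 7.2.2.1) all rest on the timing of dialysis. Only the concomitant dialysis table could change, and only through a record with a failing start date.

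**Conclusion.** The point holds as a wrong classification rule with descriptive consequences. As written, SAP 9.4.8 labels a continuing therapy prior whenever its partial start date is in an earlier year or in an earlier known month of the first-infusion year, against its own opening definition and against 7.1.4. The missing provision for ongoing therapy with a complete start date is a related defect.

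The effect is to understate on-study background therapy, such as post-transplant immunosuppression, in the concomitant medication and procedure tables, and possibly in the concomitant dialysis table, with a matching excess in the prior tables. Its size cannot be computed, because the documents give no rate of partial start dates. The planned maximum of 25 transplant recipients shows that the pattern is plausible; it is not an estimate of how many are affected. No effect is shown on the primary endpoint, on creatinine or eGFR handling, on the prohibited-treatment check or on the Per Protocol Set. The conclusion assumes that 9.4.8 is programmed as written.

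**What to change.** Bring SAP 9.4.8 into line with 7.1.4 by replacing the start-date list with an overlap rule. Class a therapy as prior only when its stop date shows that it ended before first infusion. Class it as concomitant when the stop date is on or after first infusion, when the stop date is missing, or when the therapy is ongoing, whatever the start date. Use the same wording for ongoing therapy in the complete-date branch. In the grid above, all three failing start patterns then become concomitant for continuing therapies, and those that stopped before first infusion stay prior.

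The cost is a sentence or two of SAP text and a small programming change, with slightly longer concomitant tables. The adverse event rule in 9.4.6 needs no change on this account.
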